14.3. Analysis Populations

Safety Population:

All subjects who were administered any test article excluding subjects who drop out prior to administering any test article. At least 1 observation should be recorded.

Per-Protocol (PP) Population:

All subjects who have successfully completed all visits and did not substantially deviate from the protocol as determined by the trial cohort review committee prior to database hard lock (Per-Protocol Population). Justification of excluding subjects with PDs in the Per-Protocol Population set will be documented in a memo to file.

Intent-to-Treat (ITT) Population:

All randomized subjects regardless of actual treatment and subsequent withdrawal from study or deviation from protocol.

Safety variables will be summarized on the safety population whereas efficacy variables will be summarized on the per-protocol and Intent-to-Treat population. The primary and secondary analyses will be conducted on both IIT and PP populations.

14.4. Level of Statistical Significance

All planned analysis for this study will be conducted with an overall type I error rate of 5%. Type I error will be controlled for multiplicity across interim analysis and final analysis. The operating characteristics of this adaptive trial will be provided in the SAP.

14.5. Primary Analysis

The co-primary endpoints for this study are the CLUE comfort and the CLUE vision scores evaluated after 1-week of lens wear. The primary analysis will be conducted on per-protocol and ITT populations. Both primary hypotheses must be met to meet the primary objective of the study.

CLUE Comfort and Vision scores

CLUE comfort and vision scores will be analyzed separately using a Bayesian repeated measurement random-effects model to compare between Test and Control lenses. Each regression model will include baseline values, lens type, lens wearing sequence and lens wearing period as fixed effects and investigational site as random effect. Other subject characteristics such as age, gender and will also be included as fixed effects when appropriate. Unstructured covariance matrix will be used to model the residual errors among observations within subjects. Non-informative prior distributions will be used for the coefficients in the models as well as for the error terms. Independent vague normal $N(0,1000)$ priors will be used for the regression coefficients, inverse gamma $IG(0.001, 0.001)$ for the variance of the random effect site and inverse Wishart for the residual errors. The Metropolis sampler algorithm as implemented in the SAS MCMC Procedure will be used to carry out parameter estimation. Results will be reported as regression coefficient mean estimates with credible intervals.

The null and alternative hypotheses for non-inferiority of Test lens relative to Control are as follows:

$$H_0: \Delta < -5$$
$$H_A: \Delta \geq -5$$

where Δ is the CLUE score mean difference between Test lens and Control lens (Test minus Control). Non-inferiority will be declared if the lower bound of the credible interval of the mean difference between Test and Control is greater than -5. Superiority will be declared if the lower bound of the credible interval of the mean difference between Test and Control is greater than 0. The superiority test will be performed only if non-inferiority is established.

14.6. Secondary Analysis

Average Daily Wearing Time

Average daily wear time will be analyzed using the same Bayesian model described in the primary analysis.

The null and alternative hypotheses for non-inferiority of Test lens relative to Control are as follows:

$$H_0: \Delta < -1$$
$$H_A: \Delta \geq -1$$

where Δ is the mean difference in average daily wearing time between Test lens and Control lens (Test minus Control). Non-inferiority will be declared if the lower bound of the credible interval of the mean difference between Test and Control is greater than -1. Superiority will be declared if the lower bound of the credible interval of the mean difference between Test and Control is greater than 0. The superiority test will be performed only if non-inferiority is established.

Visual Performance

Monocular distance visual performance in logMAR scale will be analyzed using a Bayesian repeated measurement random-effects model to compare between Test and Control lenses. The regression model will include baseline values, lens type, lens wearing sequence and lens wearing period as fixed effects; and investigational site and patient as random effects. Other subject characteristics such as age, gender and will also be included as fixed effects when appropriate. Unstructured covariance matrix will be used to model the residual errors among observations within same eye and subject across wearing periods. Non-informative prior distributions will be used for the coefficients in the models as well as for the error terms. Independent vague normal $N(0,1000)$ priors will be used for the regression coefficients, inverse gamma $IG(0.001, 0.001)$ for the variance of the random effect site and inverse Wishart for the residual errors. The Metropolis sampler algorithm as implemented in the SAS MCMC Procedure will be used to carry out parameter estimation. Results will be reported as regression coefficient mean estimates with credible intervals.

The null and alternative hypotheses for non-inferiority of Test lens relative to Control are as follows:

$$H_0: \Delta > 0.05$$
$$H_A: \Delta \leq 0.05$$

where Δ is the mean difference in logMAR between Test lens and Control lens (Test minus Control). Non-inferiority will be declared if the upper bound of the credible interval of the mean difference between Test and Control is less than 0.05.

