2.3. Hypotheses

Primary Hypotheses:

There are two co-primary hypotheses in this study. Both of them must be met to satisfy the primary objective of the study.

1. The Test lens will be non-inferior to the Control lens with respect to overall CLUE comfort score at the follow-up visit. A non-inferiority margin of -5 points will be used.
2. The Test lens will be non-inferior to the Control lens with respect to overall CLUE vision score at the follow-up visit. A non-inferiority margin of -5 points will be used.

Secondary Hypotheses:

1. The Test lens will be non-inferior to the Control lens with respect to average daily wear time at 1-week follow-up visit. A non-inferiority margin of 1 hour will be used.

2. The Test lens will be non-inferior to the Control lens with respect to logMAR visual performance (using ETDRS visual acuity charts) at the follow-up visit. A non-inferiority margin of 0.05 logMAR will be used.

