4. STUDY DESIGN AND RATIONALE

4.1. Description of Study Design

This study is a multi-site, group sequential, adaptive, randomized, double-masked, 2×2 crossover design, 1-week dispensing study. Subjects will wear bilaterally both Test and Control lenses in a random order for 1-week each as a daily disposable modality with a wash-out period of 1 week between the wearing periods.

Period 1:

At study Visit 1, subjects will be consented and screened for inclusion/exclusion criteria. If a subject is found to meet all eligibility criteria (see Section 34.), they will be randomly assigned to either Test/Control or Control/Test sequence using 1:1 ratio (i.e. 1/2 of subjects on the Test/Control sequence and 1/2 on the Control/Test sequence). Subjects will fit the first pair of lens in both eyes based on the sequence assigned; otherwise, the subject will be deemed ineligible for this study. Subjects will be advised to wear the study lenses at least 8 hours a day for a minimum of 6 days.

Successfully dispensed subjects at the Visit 1 will be scheduled for a follow-up visit (Visit 2). The follow-up visit will occur approximately 7 ± 2 days after the Visit 1. Unscheduled follow-up visits may occur during the study. At this visit, CLUE comfort and vision, slit lamp findings will be captured.

Wash-out period:

After completion of Visit 2, there is a 7 to 9 day washout period during which subjects may use their habitual products.

Period 2:

Following the washout period, the subject returns for Visit 3 and post-washout baseline evaluation will take place prior to lens fitting. After baseline evaluation, subject will be fitted and dispensed with the second pair of lens in the assigned sequence. Subjects will be advised to wear the study lenses at least 8 hours a day for a minimum of 6 days.

Visit 4 takes place 7 ± 2 days after Visit 3, at which CLUE comfort and vision, slit lamp findings, final evaluation will take place.

Both study lenses will be worn as a daily disposable modality. JJVC will provide the investigational sites with sufficient quantities of study lenses and supplies to complete the study.

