2.6.	Visual Acuity	Record the distance Snellen visual acuity with the contact lenses (OD, OS, and OU) to the nearest letter. Subjects must read the smallest line until at least 50% of the letters are read incorrectly.	
2.7.	Distance ETDRS LogMAR Visual Acuity	
Perform monocular distance ETDRS LogMAR visual acuity test at a 4-meter distance over the test eye only under the following conditions:
 
 • dim illumination (e.g., <2.5 lux), low luminance, with high contrast charts (LLHC) • bright illumination (e.g., >400 lux), high luminance with low contrast charts (HLLC) 
The Precision Vision 4-meter high contrast ETDRS charts (Chart 1 and Chart 2 OD, Chart 3 and Chart 4 OS) and low contrast ETDRS charts (Chart 1 and 2 OD and Chart 3 and Chart 4 OS) will be used.
 
Two measurements per condition will be performed
	
2.8.	Subjective Lens Fit Assessment	
Evaluate overall lens fit acceptance (acceptable or unacceptable) based on centration, movement and other fitting characteristics.
 
An unacceptable fit is deemed by one of the following criteria:
 
 • limbal exposure at primary gaze or with extreme eye movement • edge lift • excessive movement in primary and up gaze • insufficient movement in all three of the following conditions: primary gaze, up gaze, and Josephson push up 	

Visit 2: Treatment 1 Follow-Up Visit		
Step	Procedure	Details
		Note: if lens fit is unacceptable subject will be discontinued from the study.
2.9.	Wettability Characteristics	Record the white light lens wettability of both lenses.
2.10.	Surface Deposits	Record any front and back surface lens deposits.
2.11.	Lens Damage	Using the slit lamp, assess lenses for damage.
2.12.	Lens Removal	
The lenses will be removed and stored in the following manner:
 
The OD and OS lenses will be stored wet (using saline solution) in separate glass vials with labels that minimally contain study number, date, subject number, and eye from which the lens was removed.
 
*The lenses will be shipped back to the Sponsor ambiently once the study has completed.

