14. STATISTICAL METHODS

14.1. General Considerations

Statistical Analysis will be undertaken by the sponsor or under the authority of the sponsor. A general description of the statistical methods to be implemented in this clinical trial is outlined below. A stand-alone Statistical Analysis Plan (SAP) with more details will be finalized before the interim analysis is undertaken.

All data summaries and statistical analyses will be performed using the SAS software Version 9.4 or higher (SAS Institute, Cary, NC). Throughout the analysis of data, the results for each subject/eye will be used when available for summarization and statistical analysis. Unscheduled visits will be summarized separately and will be excluded from the statistical analysis.

Summary tables (descriptive statistics and/or frequency tables) will be provided for all baseline variables, efficacy variables and safety variables as appropriate. Continuous variables will be summarized with descriptive statistics (n, mean, standard deviation [SD], median, minimum and maximum). Frequency count and percentage of subjects or eyes within each category will be provided for categorical data.

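### As worded, the logMAR model in section 14.6 gives a subject's two eye-level lens differences zero covariance; if they are positively correlated, the non-inferiority interval is too narrow

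*Combined protocol and SAP*

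**What the plan says.** The design is a 2x2 crossover (section 4.1): "Subjects will wear bilaterally both Test and Control lenses in a random order for 1-week each". At follow-up, logMAR acuity is measured in each eye at the same visit step, with separate charts per eye (section 7.2, Visit 2: "Chart 1 and Chart 2 OD, Chart 3 and Chart 4 OS"). Section 14.1 says that "the results for each subject/eye will be used when available for summarization and statistical analysis", so the logMAR analysis has two eyes per subject per period.

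For this endpoint section 14.6 names "investigational site and patient as random effects" and describes the residuals as follows: "Unstructured covariance matrix will be used to model the residual errors among observations within same eye and subject across wearing periods". It names no subject-by-period effect, subject-by-lens effect, residual covariance between fellow eyes or cluster-robust variance.

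The CLUE model in section 14.5 has one score per subject per period, no patient effect, and a residual block set at subject level: "Unstructured covariance matrix will be used to model the residual errors among observations within subjects".

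The logMAR margin is in section 2.3 ("A non-inferiority margin of 0.05 logMAR will be used"), and the decision rule in 14.6 uses the interval alone: "Non-inferiority will be declared if the upper bound of the credible interval of the mean difference between Test and Control is less than 0.05". No credible level is attached to that interval.

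**The concern.** Moving from the CLUE model to the logMAR model, the plan shifts the residual block from subject to eye and adds a patient effect. The patient effect appears to be the intended link between the two eyes. It does link their levels. It does not link their lens differences, because it is constant over periods and drops out when Control is subtracted from Test.

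Both eyes change lens type together and are tested at the same visits. A subject's own response to a lens type, or anything about that visit that affects both eyes, would enter both differences. If so, n subjects supply less information than 2n independent differences. The credible interval would then be too narrow, and a lens that is worse by the full margin would pass more often than the nominal rate.

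**Working it through.** **Inputs.** Model terms, margin and decision rule: sections 14.6 and 2.3. Phase 1 completers: 150 (section 14.2). One logMAR value per eye per period is taken. The fellow-eye correlation of lens differences, r, and the SD of a within-eye difference are not in the documents; both are assumed and shown over a range.

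**1. Reference error level.** The plan gives no power, SD or standard error for logMAR, so there is no logMAR figure to reproduce. Table 6 (CLUE) shows which level the authors work with. For N = 150, correlation 0.5 and SD 24, the SD of the paired difference is 24 × sqrt(2 × (1 − 0.5)) = 24. With margin 5 and no true difference, a paired t-test at one-sided 2.5% has power 0.7174, against 0.717 in the table. One-sided 5% would give 0.8146. All 18 cells reproduce within 0.001 at one-sided 2.5%. That level is used below, as an inference.

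**2. What the model implies.** For subject i, eye j and period k, on the plain reading:

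y_ijk = fixed effects + site + b_i + e_ijk, with (e_ij1, e_ij2) having a 2x2 unstructured matrix R, independent between eyes.

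Let d_ij be Test minus Control for eye j. Site and b_i cancel, so Var(d_ij) = R11 + R22 − 2·R12 = Vd and Cov(d_i1, d_i2) = 0. The modelled standard error of the lens effect is sqrt(Vd / (2n)).

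**3. What holds if the differences are correlated.** With correlation r, the variance of the mean of a subject's two differences is Vd(1 + r)/2. The true standard error is therefore sqrt(Vd(1 + r) / (2n)), which is sqrt(1 + r) times the modelled one. At a true difference equal to the margin, the false non-inferiority rate is 1 − Φ(1.96 / sqrt(1 + r)). Coverage of a nominal 95% interval is 2Φ(1.96 / sqrt(1 + r)) − 1.

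| r (assumed) | true SE / modelled SE | false non-inferiority rate | coverage |
|---|---|---|---|
| −0.2 | 0.894 | 1.4% | 97.2% |
| 0 | 1.000 | 2.5% | 95.0% |
| 0.2 | 1.095 | 3.7% | 92.6% |
| 0.5 | 1.225 | 5.5% | 89.0% |
| 0.8 | 1.342 | 7.2% | 85.6% |

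**4. Does the fitted patient effect absorb the correlation?** A simulation fitted the plain-reading model by maximum likelihood (150 subjects, 1,500 runs per value). At r = 0, 0.3, 0.5 and 0.8 the ratio of empirical to modelled standard error was 0.98, 1.12, 1.22 and 1.30 (theory 1.00, 1.14, 1.22, 1.34). The false non-inferiority rate was 2.2%, 4.0%, 5.7% and 6.2% (theory 2.5%, 4.3%, 5.5%, 7.2%). The patient effect does not absorb it.

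**5. The other reading.** A 4x4 unstructured matrix over eye and period has 10 free parameters and includes every fellow-eye covariance, so the lens contrast gets the right standard error. A patient intercept would add an eleventh parameter that the data cannot separate from the matrix. It is redundant, but it does not narrow the interval.

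**6. Size on the logMAR scale.** Half-width = 1.96 × SD × sqrt((1 + r) / (2n)). With an assumed SD of 0.10 and n = 150, it is 1.96 × 0.10 × sqrt(1/300) = 0.0113 at r = 0 and 1.96 × 0.10 × sqrt(1.5/300) = 0.0139 at r = 0.5, a gap of about 0.0025. With SD 0.15 the gap is about 0.004.

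**The case against.** The strongest reply is that the text does not fix one model. The residual sentence names both eye and subject and can be read as one matrix per subject over eye and period, in which case nothing is understated. The priors listed in 14.6 lend this some support: there is one for the site variance and one for the residual matrix, but none for a patient variance. That list could also have been carried over from 14.5. The per-eye reading remains the plainer one, because it gives the patient effect a purpose.

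Second, section 14.1 calls the chapter a general description and defers detail to a stand-alone SAP, which is not in the text reviewed. That SAP is a natural place to settle the block structure. The deferral does not cure the model already written, and section 14.10 says the analysis will follow these sections.

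Third, r is unknown. Separate charts, separate lenses and separate letter-reading noise for each eye pull it towards zero, and a baseline value taken in each period might absorb some shared state. This stands, so the size can only be given as a range.

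Fourth, the practical effect is small: the decision changes only if the estimate falls in a band a few thousandths of a logMAR wide. This also stands, under the assumed SDs.

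A reader might infer that the interval is certain to be too narrow, or that the 0.05 logMAR claim has a known inflated error rate. The documents do not support either: they give no r, the wording allows a sound reading, and the 2.5% reference is inferred from a table for another endpoint. A reader might also assume that one examiner tests both eyes at both visits; section 7.2 does not say so.

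**Conclusion.** The point holds in conditional form. On the plain reading of 14.6, a subject's two eye differences are modelled as independent. The modelled standard error is then too small by a factor of sqrt(1 + r) whenever r is above zero. Positive r is plausible, because both eyes share the visits and the lens type, but it is an assumption. Over r from 0 to 0.8 the false non-inferiority rate at the margin runs from the nominal 2.5% to about 7.2%. At negative r the test is conservative instead. On the 4x4 reading the interval is correct, and the only fault is a superfluous term.

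The consequence is limited to interval coverage and the error rate for one secondary hypothesis. The primary objective rests on the two CLUE scores, which are not affected. The model line should still be corrected, since the text most naturally describes the weaker model and the better one is easy to state.

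**What to change.** In section 14.6, and in the stand-alone SAP before the interim analysis, replace the covariance description for logMAR with one of these:

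- a single 4x4 unstructured residual matrix over eye by period within subject, with no patient random effect; or
- the patient effect and per-eye matrix as now, plus a subject-by-period random effect.

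The first also allows for negative r. The second implies a fellow-eye covariance of differences equal to twice the subject-by-period variance, so it allows only r of zero or more. If the patient effect is kept, give its variance a prior.

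The cost is one model line in the text and the code, and possibly a slightly wider interval. With the correct standard error, 150 subjects and no true difference, power = Φ(0.05/SE − 1.96). For an assumed within-eye difference SD of 0.10 to 0.15 logMAR this is at least 98% even at r = 1. At an assumed SD of 0.20 it is 99% at r = 0, 94% at r = 0.5 and 86% at r = 1.

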14.7. Other Analyses

A subgroup analysis will be conducted by considering only subjects who are habitual users of 1-Day ACUVE Moist. Further exploratory analysis will be conducted if necessary at the discretion of the Study Responsible Clinician.

14.8. Interim Analysis

This is a group sequential adaptive trial with stopping rules for non-inferiority and superiority. The study will be conducted in two phases. In Phase 1, up to 160 subjects will be enrolled with a target completion of 150. The data from Phase 1 will then be analyzed to see if non-inferiority/superiority can be concluded. The following stopping rules will be considered:

- If non-inferiority can be concluded, test for superiority. If superiority can be concluded stop the study for early success. Otherwise, calculate the predictive probability (PP) of superiority. If $PP < 0.20$, stop the study. If $PP \geq 0.80$, continue the trial and recruit the Phase 2.
- If non-inferiority can't be concluded. Calculate the PP of non-inferiority. If $PP < 0.20$, stop the study. If $PP \geq 0.80$, continue the trial and recruit the Phase 2.

More details will be provided in the SAP.

14.9. Procedure for Handling Missing Data and Drop-Outs

Missing or spurious values will not be imputed. The count of missing values will be included in the summary tables and listings.

Subject dropout is expected to be one of the main reasons of missing data in this clinical trial. Past clinical trials don't provide the evidence that subject dropout is systematic or not-at-random. To evaluate the impact of missing data, sensitivity analysis may be considered by automatically sampling all missing values and incorporating them in the Markov chain for the parameters using the PROC MCMC procedure.

14.10. Procedure for Reporting Deviations from Statistical Plan

The analysis will be conducted according to that specified in above sections. There are no known reasons for which it is planned to deviate from these analysis methods. If for any reason a change is made, the change will be documented in the study report along with a justification for the change.

15. DATA HANDLING AND RECORD KEEPING/ARCHIVING

15.1. Electronic Case Report Form/Data Collection

The data for this study will be captured on electronic case report forms (eCRFs) using an EDC system from Bioclinica. An authorized data originator will enter study data into the eCRFs using

the EDC system. Data collected on equipment that is not captured in EDC will be formatted to the specification of the JJVC database manager and sent to JJVC for analysis.

External Date Sources for this study include: Not Applicable

The clinical data will be recorded on dedicated eCRFs specifically designed to match the study procedures for each visit. Once completed, the eCRFs will be reviewed for accuracy and completeness and signed by the Investigator. The sponsor or sponsor's representatives will be authorized to gain access to the subject recordation for the purposes of monitoring and auditing the study.

Edit checks, electronic queries, and audit trails are built into the system to ensure accurate and complete data collection. Data will be transmitted from the clinical site to a secure central database as forms are completed or updated, ensuring information accuracy, security, and confidentiality. After the final database lock, the Investigator will be provided with Individual Patient Profiles (IPP) including the full audit trail on electronic media in PDF format for all of the study data. The IPP must be retained in the study files as a certified copy of the source data for the study.

The content and structure of the eCRFs are compliant with ISO14155:2011.¹

